EVITA

EVAluation of cardiac magnetic resonance Imaging (MRI) in follow up assessmenT of patients with pulmonary Arterial hypertension (PAH)
Prospective cohort study of *cardiac MRI in PAH*

STATISTICAL ANALYSIS PLAN

[name] / [name]

15th of December 2020

Sponsor: Centre Hospitalier Régional Universitaire de Nancy

Identifiers: NCT02845518 **Unique Protocol ID:** PHRC-15-0210

Principal Coordinator / Central Contact Person: [name] [name]

Methodologists and statisticians: [name] & [name]

I/ General considerations:

The 2-tailed significance level will set to $p < 0.05$.

II/ Descriptive analysis

Continuous variables will be expressed as mean \pm SD or as median (25-75 percentile) as appropriate. Categorical variables will be expressed as frequencies (percentages).

III/ Analyses to respond to main objective:

The aim of the trial is to assess the sensitivity and specificity cardiac magnetic resonance imaging (cMRI) regarding the diagnosis of hemodynamic criteria for intermediate risk or high-risk status determined from right heart catheterization (RHC) measurements. There will be 3 time-points: baseline, between 3 and 6 months and 24 months.

The outcome variable will consequently be hemodynamic criteria for intermediate risk or high-risk status defined as a cardiac index (CI) $< 2.5 \text{ l/min/m}^2$ or right atrial pressure $> \text{ or } = 8 \text{ mm Hg}$. This definition is in line with the last ESC/ERS guidelines for diagnosis and treatment of pulmonary hypertension (1).

The cMRI exposition variable will be defined as a cMRI CI $< 2.5 \text{ l/min/m}^2$ or a right ventricle ejection fraction (RVEF) $< 35\%$ or an absolute decrease of 10% of RVEF at a follow-up evaluation (for the second and third time-point).

Sensitivity, specificity and their exact 95% confidence intervals will be computed using the binomial distribution.

However, by nature, 3 tests will be performed for each subject unless they experience death or are unable to perform one (or more) test during the follow-up. The repeated nature of the data will be considered including a random effect in the analyses. We will construct a logistic regression model with hemodynamic criteria for intermediate risk or high-risk status as outcome and cMRI dichotomous variable as exposure using a random effect at the patient level (2). The glmer command from the lme4 package will be used (R package, CRAN). Sensitivity and specificity and their confidence interval will then be extracted from the logistic model.

This analysis will consequently provide the overall (i.e. across the 3 time-points) sensitivity and specificity of cMRI integrated aforementioned exposition variable for the integrated aforementioned RHC definition taking into account the repeated nature of the data.

In addition, the following secondary analyses will be performed:

- sensitivity and specificity evaluation of cMRI integrated exposition variable for the integrated RHC at each time points (i.e. at baseline, 3-6 months and 24 months),
- sensitivity and specificity evaluation for each component of the RHC definition (i.e. considering only cardiac index $< 2.5 \text{ l/min/m}^2$ or only right atrial pressure $> \text{ or } = 8 \text{ mm Hg}$) and cMRI definition (i.e. considering only cMRI CI $< 2.5 \text{ l/min/m}^2$ or only RVEF $< 35\%$ or only absolute decrease of 10% of RVEF at a follow-up evaluation) overall and at each time-points.

In addition, parametric or non-parametric correlation analyses (depending on variable distributions) will also be performed for cMRI CI and RHC CI.

IV/ Analyses of Secondary objectives

Secondary objectives 1 and 2:

- 1) To assess the predictive value of the first occurrence of morbimortality events in 2 different analyses derived from RHC criteria (cardiac index (CI) $< 2.5 \text{ l/min/m}^2$ or a right atrial pressure $= \text{ or } > 8 \text{ mm Hg}$) and from cMRI criteria (CI $< 2.5 \text{ l/min/m}^2$ or RVEF $< 35\%$ or an absolute decrease of 10% of RVEF at a follow-up evaluation).
- 2) To assess the univariable association between first morbimortality events occurrence and NYHA functional class, 6-minute walk distance, plasma level of BNP/NT-proBNP, and continuous hemodynamic variables from cMRI, RHC and echocardiography data collected at baseline and after 3-6 months of follow-up.

The morbimortality event will be defined as the composite endpoint of

- 1 Death from any cause
- 2 Lung transplantation
- 3 Atrial septostomy
- 4 Worsening of PAH defined by all three following criteria: a decrease in the 6-minute walk distance of at least 15 % from baseline (or unable to perform the test), a worsening of PAH symptoms and an unscheduled hospitalization (or an increase in the length of stay in the hospital) due to PAH

The following exposition variables will be used:

- RHC and cMRI definition used in the primary analysis
- Components of the RHC and cMRI definitions
- Additional RHC variables: stroke volume index, mean pulmonary arterial pressure, pulmonary vascular resistance, SvO_2 , pulmonary arterial compliance (stroke volume divided by pulse pressure)
- Additional cMRI variables: stroke volume index, right ventricular end-systolic volume index, right ventricular end-diastolic index, right ventricular end-systolic volume divided by stroke volume as an estimate of right ventriculo-arterial coupling
- Echocardiography variables: pericardial effusion, TAPSE $< 18 \text{ mm}$, right atrium area $= \text{ or } > 18 \text{ cm}^2$.

Proportional hazard analysis

Association between factors and time to first occurrence of events will be assessed using Cox proportional hazard regression. Both univariable and multivariable analyses will be performed. The validity of the assumptions of the Cox models will be checked: proportional hazards, log-linearity, absence of interaction and collinearity.

The adjusted analyses will be adjusted for NYHA class, 6-minute walk distance and natriuretic peptides. Additional adjustment factors found significant will also be entered in a multivariable analysis after stepwise forward-backward selection using a 0.05 threshold.

Importantly, the aforementioned RHC and MRI definitions will be first used as exposition variables.

In addition, the components of each definition and additional cMRI variables will also be used as individual exposition variables.

Associations between echocardiography variables and outcome will also be evaluated.

Three sets of analyses will be provided. The first one will assess the association of baseline data with subsequent outcome, the second one will assess the association of 3-6 months data with subsequent and the last model will assess the association of baseline and 3-6 months data with outcome using a time-dependent Cox-model. In this time-dependant Cox model, association of baseline data will be considered until the 3-6 months data is acquired; association with outcome after the 3-6 months evaluation will be assessed using the 3-6 months data.

For each model, the predictive value will be assessed using C-index and NRI (3). In addition, changes in C-Index and NRI will also be evaluated comparing models including only covariates, including covariates and RHC data, including covariates and MRI data and including covariates, RHC and MRI data. This strategy has been used previously by our group (4).

Importantly, as sensitivity analyses,

- repeated events will be considering using a negative binomial model (5-7). This survival analysis will account for the occurrence of multiple events during the follow-up,
- the associations with the components of the composite endpoint will be assessed.

Secondary objective 3:

3) To assess the multivariable association between first morbimortality events occurrence and the above factors, identifying clinical and hemodynamic variables independently contributing to prognosis. Using the results of this analysis we plan to build a multiparameter prognostic score.

Two survival models will be used in this analysis, as mentioned above: Cox survival model (for first events) and negative binomial analysis as sensitivity analysis (accounting for repeated events).

Candidate variables for this analysis are the one mentioned for the analysis of secondary objective 1 and 2. A stepwise selection procedure will be used, retaining in the analysis only factor associated with a $p < 0.05$ with the outcome.

Internal validation of the multivariable model and of the score which could be derived from it will be performed using the bootstrap method described by Harrell *et al* (8). Importantly, variables will be used both as dichotomized variables (using the cut-offs used in the primary objective) and as continuous variables. In case a continuous variable should be dichotomized for lack of log-linearity, the cutpoint will be validated in the same bootstrap resamples as for the model and score. In addition, optimal cutpoints will also be assessed on the continuous variables based on C-index maximization (9).

Secondary objectives 4:

4) To quantify complications due to cMRI and to RHC.

This will be mostly a descriptive analysis. The overall frequency of reported adverse events and severe adverse events will be compared between groups using the Chi-Square test (or Fisher's exact test where requested). In addition, to account for the paired nature of the data, a McNemar test will be performed.

Secondary objectives 5:

5) To determine the magnitude of better tolerability of cMRI over RHC for the patient.

Physical and psychological distress due to cMRI and RHC will be measured with questionnaires.

The comparison of the Likert-type scales of the questionnaires will be carried out using the Chi-Square test.

Secondary objective 6:

6) To create a biobank for diagnosis and prognosis purposes This study is a prospective cohort study. PAH patients will be recruited in 20 centers of the French network of severe pulmonary hypertension.

Blood samples to obtain DNA at one visit from circulating blood cells and plasma at all visits with MRI.

References

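### The clustered model for the main objective regresses RHC status on the cMRI result, so it yields predictive-value quantities rather than sensitivity and specificity, and no conversion is given

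*SAP*

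**What the plan says.** Section III of the SAP (analyses for the main objective) sets the aim as the accuracy of cMRI against right heart catheterization. It assigns the roles before any model appears: "The outcome variable will consequently be hemodynamic criteria for intermediate risk or high-risk status", with the cMRI criteria as the exposure. It then plans a simple calculation: "Sensitivity, specificity and their exact 95% confidence intervals will be computed using the binomial distribution".

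The section goes on to note that each patient contributes up to three tests. To handle this it specifies a "logistic regression model with hemodynamic criteria for intermediate risk or high-risk status as outcome and cMRI dichotomous variable as exposure", with a random effect at the patient level, fitted with glmer and citing reference 2. Two statements follow: "Sensitivity and specificity and their confidence interval will then be extracted from the logistic model" and "This analysis will consequently provide the overall (i.e. across the 3 time-points) sensitivity and specificity". The second gives the overall result to this model. No formula for the extraction, no averaging over the random effect and no interval method are stated.

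**The concern.** Sensitivity is P(cMRI+ | RHC+) and specificity is P(cMRI− | RHC−): both condition on the reference standard. The model in section III conditions on the index test. Its two fitted probabilities are P(RHC+ | cMRI+), a PPV-type quantity, and P(RHC+ | cMRI−), a 1 − NPV-type quantity. Without averaging over patients, they also hold only for a patient whose random effect is zero.

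At stake is the overall answer to the main objective. If the model's probabilities were reported under the names sensitivity and specificity, they would shift with the share of RHC-positive visits even if cMRI accuracy were constant. They could also disagree with the exact binomial figures under the same names, and the SAP does not say what to do then.

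**Working it through.** **Inputs.** The roles of the variables, the model form and the extraction statement come from SAP section III. The SAP gives no sample size, prevalence or expected accuracy, so there is no planned figure to reproduce. Every accuracy, prevalence and standard deviation below is an assumption.

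**Step 1: what the model estimates.** As written, logit P(RHC+ | cMRI, u) = b0 + b1·cMRI + u, where u is the patient effect. Leaving u aside, expit(b0 + b1) = P(RHC+ | cMRI+) = PPV and 1 − expit(b0) = P(RHC− | cMRI−) = NPV. The random intercept does not alter which variable is conditioned on.

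**Step 2: size of the direction error.** With prevalence p, sensitivity Se and specificity Sp:

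- PPV = p·Se / [p·Se + (1 − p)(1 − Sp)]
- NPV = (1 − p)·Sp / [(1 − p)·Sp + p(1 − Se)]

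For Se = 0.85 and Sp = 0.75:

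| p | PPV | in place of Se 0.85 | NPV | in place of Sp 0.75 |
|---|---|---|---|---|
| 0.30 | 0.255/0.430 = 0.593 | −26 points | 0.525/0.570 = 0.921 | +17 points |
| 0.50 | 0.425/0.550 = 0.773 | −8 points | 0.375/0.450 = 0.833 | +8 points |
| 0.60 | 0.510/0.610 = 0.836 | −1 point | 0.300/0.390 = 0.769 | +2 points |
| 0.80 | 0.680/0.730 = 0.932 | +8 points | 0.150/0.270 = 0.556 | −19 points |

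**Step 3: check by fitting.** Logistic models without the random effect were fitted to expected 2×2 tables with assumed Se 0.90 and Sp 0.80. In the SAP's direction they returned 0.529/0.970 at prevalence 0.2, 0.659/0.949 at 0.3, 0.818/0.889 at 0.5 and 0.913/0.774 at 0.7. With the variables swapped they returned 0.900/0.800 at every prevalence. The odds ratio was (0.9/0.1) × (0.8/0.2) = 36 in both directions: it survives the swap, but the probabilities do not.

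**Step 4: what a conversion would need.** With q = P(cMRI+), Se = PPV·q / [PPV·q + (1 − NPV)(1 − q)]. In the p = 0.50 row, q = 0.550, so Se = 0.425 / (0.425 + 0.167 × 0.450) = 0.425/0.500 = 0.85. The conversion works, but a regression of RHC status on cMRI does not estimate q, and the SAP names no such step.

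**Step 5: with repeated visits.** A simulation used 200 data sets of 180 patients and 3 visits. RHC-positive shares were 75%, 45% and 45%. The random-intercept SD was 2 for RHC status and 1 for cMRI given RHC.

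| Quantity | first value | second value |
|---|---|---|
| Crude sensitivity / specificity | 0.851 | 0.751 |
| Crude PPV / NPV | 0.805 | 0.806 |
| SAP's model, averaged over patients | 0.795 | 0.793 |
| SAP's model, at random effect zero | 0.871 | 0.869 |
| Swapped model, averaged over patients | 0.850 | 0.751 |
| Swapped model, at random effect zero | 0.885 | 0.789 |

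The direction error here is 0.795 − 0.851 = −0.056 and 0.793 − 0.751 = +0.042. Reading the SAP's model at random effect zero adds about 0.076 to each value, which is a separate problem.

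**The case against.** **The extraction could mean something else.** The SAP never says that the fitted probabilities themselves will be reported. A statistician might dichotomise the fixed-effect predictions and cross them with RHC status. With one binary predictor and a positive slope, a cut between the two predicted values returns the cMRI result itself, and so the crude sensitivity and specificity. This is fair: that PPV and NPV would be reported is the natural reading, not a certainty. But this route gives no cluster-adjusted interval, which is what the model was introduced to supply. If the predictions include the patient effects, each patient's own RHC results enter the prediction. In a simulation under the Step 5 assumptions (60 data sets), a 0.5 cut-off then gave 0.884/0.811 against crude 0.847/0.747.

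**Reference 2 may contain the method.** By its title it is a tutorial on exactly this problem, and it may cover averaging and intervals. Its content is not in the SAP, and a citation does not override an outcome and exposure written out in the text.

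**The exact binomial estimates are correctly directed.** They are, and the analyses at each time-point need no repeated-measures model. Pooled over visits, however, they ignore the repeated tests, and the SAP gives the overall result to the model.

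**The largest errors come from extreme prevalences.** True: the clustered simulation gives about 6 and 4 points. The size is unknown until the data are seen.

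**The swapped model was tested on data of its own form.** Also true. When a shared patient severity drove both tests, its averaged values departed from the crude ones by up to 2 points in the scenarios tried. That favours marginal proportions over the swapped mixed model; it does not rescue the stated one.

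**Conclusion.** The point holds and needs correcting. The clustered model runs in the wrong direction for the stated aim, and the step that would repair it is absent. That conclusion rests on the SAP's wording alone. The size rests on assumptions: with sensitivity 0.85 and specificity 0.75, the error runs from −26 to +8 points for sensitivity and from +17 to −19 points for specificity as prevalence goes from 0.30 to 0.80. It is nearly nil around 0.60, so plausible-looking output is no reassurance. The binomial analyses at single time-points are not affected.

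**What to change.** Rewrite the repeated-measures paragraph of section III in one of two ways, and name the chosen one as the overall result:

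- **Swapped mixed model.** Make the cMRI result the dependent variable and RHC status the covariate, with the patient random effect. Report P(cMRI+ | RHC+) and 1 − P(cMRI+ | RHC−), each averaged over the random-effect distribution, with a 95% interval from a bootstrap that resamples patients.
- **Marginal proportions.** Estimate the same two proportions directly, with GEE or cluster-robust intervals on patient. This depends less on the form of the random effect.

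If the mixed model is kept, the averaging must be written down. With marginal values of 0.85 and 0.75, reading the swapped model at random effect zero gives 0.886/0.788 for an assumed random-intercept SD of 1, and 0.940/0.856 for an SD of 2.

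Keep the exact binomial intervals for the analyses by time-point, where each patient counts once. Apply the chosen clustered method to the overall component analyses as well. The cost is a sentence or two in the SAP and a few lines of code, with no new data.

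### Paired cMRI and RHC cardiac index values are compared only by correlation, which cannot show an offset at the shared 2.5 l/min/m² cut-off; add bias and limits of agreement

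*SAP*

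**What the plan says.** Section III defines the reference status by "hemodynamic criteria for intermediate risk or high-risk status defined as a cardiac index (CI) $< 2.5" l/min/m², or a raised right atrial pressure. The index test starts the same way: "The cMRI exposition variable will be defined as a cMRI CI" below 2.5 l/min/m², or a right ventricular ejection fraction criterion. The main analysis is the sensitivity and specificity of the two composite definitions over three time-points. Secondary analyses repeat this by time-point and include a "sensitivity and specificity evaluation for each component of the RHC definition" and of the cMRI definition.

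For CI as a continuous measurement, Section III closes with one sentence: "parametric or non-parametric correlation analyses (depending on variable distributions) will also be performed for cMRI CI and RHC CI". The SAP contains no mean paired difference, limits of agreement, concordance coefficient or calibration regression.

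Three other statements bear on the point:

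- Section II lets continuous variables be summarised as mean and SD "or as median (25-75 percentile) as appropriate".
- Section III expects three tests per patient "unless they experience death or are unable to perform one (or more) test during the follow-up".
- Section III states that "The repeated nature of the data will be considered including a random effect in the analyses". The next sentence specifies the logistic model for sensitivity and specificity. Whether the random effect also covers the correlation is not stated.

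**The concern.** When one absolute cut-off is applied to two measurement methods, a systematic difference between them matters directly. If cMRI reads higher than RHC, patients with a low RHC CI are missed; if it reads lower, patients are flagged wrongly. Pearson and Spearman coefficients are both unchanged by a constant offset or by a positive rescaling of one method, so a high correlation can sit beside systematic misclassification at 2.5.

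What is at stake is interpretation. If cMRI CI performs poorly against RHC CI in the component analysis, readers will ask whether the cause is a shift, which recalibration or another cut-off could address, or scatter, which neither would remove. The analysis named for the paired values cannot show the shift.

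**Working it through.** **Inputs.** From the SAP: a cut-off of 2.5 l/min/m² on both methods, up to three pairs per patient, and correlation as the only analysis of the paired continuous values. The SAP gives no CI mean, SD, measurement error, correlation or number of pairs, so there is no plan figure to reproduce. Every distributional value below is an assumption.

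**Model.** RHC CI = T + e1 and cMRI CI = T + d + e2, all normal, with d a constant offset. Base case: T has mean 2.6 and SD 0.65; e1 and e2 each have SD 0.25.

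**Step 1: correlation.** r = 0.65² / (0.65² + 0.25²) = 0.4225 / 0.485 = 0.871. The offset d does not enter.

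**Step 2: classification at 2.5.** From the bivariate normal distribution, for cMRI CI < 2.5 against RHC CI < 2.5:

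| Offset d (l/min/m²) | r | Sensitivity | Specificity |
|---|---|---|---|
| −0.3 | 0.871 | 0.949 | 0.654 |
| −0.1 | 0.871 | 0.873 | 0.797 |
| 0 | 0.871 | 0.817 | 0.855 |
| +0.1 | 0.871 | 0.750 | 0.902 |
| +0.3 | 0.871 | 0.591 | 0.962 |

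**Step 3: range.** 27 sets were run: mean 2.3, 2.6 or 2.9; true SD 0.5, 0.65 or 0.8; error SD 0.15, 0.25 or 0.40. Across sets r runs from 0.61 to 0.97, but it is constant within each set whatever the offset.

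| Offset d | Loss across the 27 sets |
|---|---|
| +0.1 | sensitivity 0.04 to 0.12 |
| +0.3 | sensitivity 0.14 to 0.39 |
| −0.1 | specificity 0.04 to 0.11 |
| −0.3 | specificity 0.12 to 0.36 |

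A separate set of assumptions (mean 2.5, SD 0.7, r = 0.8) gives the same pattern: 0.795/0.795 with no offset and 0.593/0.925 at +0.3. In simulated pairs under those assumptions, shifts of −0.5, 0 and +0.5 left Pearson at 0.800 and Spearman at 0.785.

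**Step 4: can the bias be recovered from other planned outputs?** If means, SDs and Pearson r were all reported on the same pairs, yes. Each SD is √0.485 = 0.696. The SD of differences is √(0.696² + 0.696² − 2 × 0.871 × 0.696²) = 0.354, and the limits are bias ± 1.96 × 0.354 = ± 0.69. The SAP does not commit to this: it allows medians with quartiles, a rank correlation, and missing tests. If cMRI alone were missing at 10% to 20% of visits, and CI at those visits were lower by 0.3 to 0.6, the difference in means would show an apparent offset of 0.1 × 0.3 = 0.03 to 0.2 × 0.6 = 0.12 with no true offset.

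**Step 5: precision of the direct estimate.** With 100 independent pairs (assumed), the 95% half-width is 1.96 × 0.354 / √100 = 0.07 for the bias, and 1.96 × 0.354 × √(1/100 + 1.96²/(2 × 99)) = 0.12 for each limit. With three visits per patient and a within-patient correlation ρ of the differences of 0.2 to 0.6, treating pairs as independent makes the overall standard error too small by √(1 + 2ρ) = 1.18 to 1.48.

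**The case against.** The strongest reply is that this is a diagnostic accuracy study and the SAP does not present correlation as an agreement analysis. The sentence is a closing addition tied to no claim of interchangeability. The component analysis already responds to an offset. In the base case, false negatives and false positives, as shares of all pairs, go from 8.1% and 8.1% with no offset to 18.1% and 2.1% at +0.3. An imbalance of that size would be visible in the two-by-two table.

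Much of this stands. The primary and component analyses are unaffected, the table would show the direction of a large offset, and the magnitudes above are assumed. The missing-visit scenario is also hypothetical: a visit that loses both tests leaves the pairs matched.

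It does not remove the point. The two-by-two table gives no estimate in l/min/m² and no confidence interval, and unequal measurement error can also unbalance it. Shift and scatter can give the same sensitivity: in the base case about 0.75 arises from a +0.1 offset, or with no offset from raising the cMRI error SD from 0.25 to 0.50. Specificity then differs (0.90 against 0.78), and r would fall to 0.74, but these are clues to be pieced together, not an estimate. The SAP chose to compare the paired values and named a statistic that cannot detect the error most relevant to a shared cut-off.

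**Conclusion.** The concern holds as a worthwhile improvement; it does not threaten the primary result. Two facts rest on the document alone: both definitions share the 2.5 l/min/m² cut-off, and correlation is the only analysis named for the paired continuous values. Its insensitivity to an offset is mathematical and needs no assumption. How far an offset would move the CI component's sensitivity and specificity depends on the assumed distributions, and whether one exists is unknown. The consequence is limited to how the CI comparison is reported and how the component results are explained.

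**What to change.** In Section III, make a Bland-Altman analysis the main comparison of continuous cMRI CI and RHC CI:

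- Report the mean paired difference and the 95% limits of agreement, each with a 95% confidence interval, at each time-point and overall, on visits where both values are available.
- Use a patient random effect for the repeated pairs in the overall estimate.
- Keep correlation as a descriptive supplement by time-point.
- Show the plot of difference against mean, with a note that a non-zero slope is not by itself evidence of level-dependent bias. Unequal measurement error alone produces one: with error SDs of 0.40 (RHC) and 0.15 (cMRI), the slope is [(0.15² − 0.40²)/2] / [true SD² + (0.15² + 0.40²)/4], which is −0.23 at a true SD of 0.5 and −0.10 at 0.8.

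The cost is SAP wording and one extra table or plot on data already collected, plus the caveat on reading the slope. The sensitivity and specificity analyses stay as they are.

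### Analyses of 3-6 month predictors keep a walk-distance criterion anchored at study baseline, so early walk change can inflate their apparent prognostic value

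*SAP*

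**What the plan says.** Section III of the SAP names the visits: "There will be 3 time-points: baseline, between 3 and 6 months and 24 months". Baseline is thus a separate visit from 3-6 months.

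Section IV, under secondary objectives 1 and 2, gives one composite event: death, lung transplantation, atrial septostomy, or "Worsening of PAH defined by all three following criteria". The first criterion is "a decrease in the 6-minute walk distance of at least 15 % from baseline (or unable to perform the test". The other two are "a worsening of PAH symptoms and an unscheduled hospitalization (or an increase in the length of stay in the hospital) due to PAH". Only the walk criterion has a stated reference visit.

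The predictors include NYHA class, walk distance, natriuretic peptides and "continuous hemodynamic variables from cMRI, RHC and echocardiography data collected at baseline and after 3-6 months of follow-up". Three sets of Cox analyses follow. In the second, "the second one will assess the association of 3-6 months data with subsequent" (the sentence stops there; by parallel with the first set, the missing word is outcome). The third is a time-dependent model that switches to the 3-6 month values once they are available. Neither has its own event definition.

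On covariates, the SAP says: "The adjusted analyses will be adjusted for NYHA class, 6-minute walk distance and natriuretic peptides". It does not say which visit's walk distance is meant.

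**The concern.** The second set, and the third after the visit, update the predictor but not the reference for the outcome. Part of the outcome is then fixed by what happened before time zero. Two patients with the same later hospitalisation, symptom worsening and proportional loss of walking capacity can be classified differently, only because one had declined and the other had improved by 3-6 months.

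For 3-6 month walk distance as a predictor the link is direct. For RHC and cMRI markers it runs through any correlation with early walk change. The follow-up cMRI definition includes an absolute RVEF decrease and the RHC definition has no change element, so the link need not be equally strong for the two tests. The SAP gives no figure to settle this.

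At stake are the hazard ratios, C-index and NRI comparisons for 3-6 month data, and any prognostic score under secondary objective 3 that uses them. The primary sensitivity and specificity analysis is not touched.

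**Working it through.** The SAP states no event rate, effect size or sample size on this point, so there is no figure of its own to reproduce.

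**Threshold arithmetic (from the SAP's 15% alone).** Let B be the baseline walk and M the 3-6 month walk. The event line is 0.85 × B. The further fall needed from M is max(0, 1 − 0.85 × B / M). With B = 300 m the line is 0.85 × 300 = 255 m:

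- M = 250 m: 255/250 = 1.02, so no further fall is needed.
- M = 300 m: 1 − 255/300 = 15%.
- M = 400 m: 1 − 255/400 = 36%.

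**Size, first set of assumptions (none from the SAP).** In a simulation, hospitalisation and death were made independent of 3-6 month status, so the true hazard ratio is 1. Inputs: 40% test-positive; baseline walk 380 m (SD 100); change to 3-6 months +10% (SD 20%); fall at hospitalisation 20% (SD 15%) of the current level; hospitalisation 0.15/year; death 0.06/year; 20 months of follow-up. A hospitalisation met the walk criterion in about 0.97 of patients at least 15% worse at 3-6 months and about 0.19 of those at least 15% better. Hazard ratio of a positive test on death plus worsening:

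| Correlation of marker with early walk change | Unadjusted | Adjusted for 3-6 month walk only |
|---|---|---|
| 0.2 | 1.11 | 1.08 |
| 0.4 | 1.24 | 1.16 |
| 0.6 | 1.38 | 1.26 |

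**Size, second set of assumptions.** Baseline walk 380 m (SD 100); change +30 m (SD 50); fall at hospitalisation 15% (SD 15%); 10% unable to walk; hospitalisation 0.12/year over 1.6 years; other components 0% or about half of events. Hazard ratios per SD, true value again 1:

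- Imaging marker, correlation 0: about 0.99.
- Imaging marker, correlation 0.3: 1.14 (all events worsening) or 1.06 (half).
- Imaging marker, correlation 0.5: 1.26 or 1.12. Adjusted for 3-6 month walk only: 1.23 or 1.10.
- Lower 3-6 month walk distance itself: 1.19-1.20 or 1.08-1.10.

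**What dilutes it.** First set, correlation 0.4, unadjusted value 1.24:

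- 30% unable to walk: 1.14.
- 50% unable to walk: 1.09.
- Mean fall 35% instead of 20%: 1.13.
- 30% unable and other-component hazard 0.10/year: 1.11 (1.06 at correlation 0.2).

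In the second set at correlation 0.5 with half of events worsening, 50% unable to walk or a mean fall of 35% brings 1.12 down to about 1.04-1.05.

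**Possible remedies.** Adjusting for both baseline and 3-6 month walk, with the event unchanged, held the marker's ratio at 0.99-1.03. Referencing the walk criterion to the 3-6 month value gives 1.00 if the early change fully persists until hospitalisation. At correlation 0.4 it gives about 0.88 if half persists and 0.82 if none does. The baseline-referenced ratios in those two cases are 1.14 and 1.00.

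**The case against.** The strongest reply is that the fixed reference is a legitimate choice. Being hospitalised, more symptomatic and at least 15% below entry is a clear state, and asking whether 3-6 month data predict it is coherent. One definition also keeps the three analysis sets comparable. This stands, and is why the baseline-referenced event should remain the main definition.

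A reader might infer that the plan must produce spurious prognostic value at 3-6 months. The SAP does not support that. All three worsening criteria are needed, so a low 3-6 month walk alone is not an event. "Death from any cause", transplantation and septostomy have no walk reference. Inability to walk meets the criterion whatever the reference. RHC and cMRI markers are affected only through a correlation that the SAP does not give.

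A reader might also infer that the event should simply be re-anchored at 3-6 months. The result of exactly 1.00 after re-anchoring depends on drawing the later fall from the 3-6 month level. If early change fades or is partly measurement noise, re-anchoring errs the other way: with 12% test noise, the event rate ratio for the lowest against the highest third of 3-6 month walk distance was 0.86.

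The SAP's planned component analyses help, since three of the four components are free of the problem. They do not repair the worsening component or the composite models.

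**Conclusion.** The coupling follows from the SAP's text and from arithmetic on its 15% threshold; no assumption is needed for that. Its size does rest on assumptions. For a marker without true effect, the hazard ratio is about 1.05 to 1.4 over the inputs tried (per SD or positive against negative test, depending on the set), and 1.0 at zero correlation with early walk change. The high end needs a correlation near 0.6, nobody unable to walk, and moderate falls at hospitalisation.

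The bias is therefore possible rather than certain. It is direct for 3-6 month walk distance and indirect for RHC and cMRI. It concerns secondary objectives only. It merits action because adjustment for 3-6 month walk distance alone, which is one reading of the SAP's covariate rule, leaves most of it in place: 1.16 of 1.24, or 1.23 of 1.26.

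**What to change.** In section IV of the SAP:

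1. Keep the baseline-referenced event as the main definition in all three sets, and state that its reference is the study baseline walk test also for events after the 3-6 month visit.
2. In the second set and the post-visit period of the time-dependent model, adjust for both baseline and 3-6 month walk distance instead of one unspecified value. This protects the RHC and cMRI estimates. The coefficient of 3-6 month walk distance itself still carries the coupling and should be read with item 3.
3. Add a sensitivity analysis with the walk criterion referenced to the 3-6 month walk distance, labelled as one that can err in the opposite direction if the early change does not persist.
4. Base claims of 3-6 month prognostic value on agreement between the two versions and with the walk-free components (death, transplantation, septostomy).

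The cost is one more covariate and one more derived event variable. The walk distances concerned are already predictors or event criteria in the SAP.
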